In the same review from 2008-2013, fourteen infants arrived to the PICU with temperatures above 38°C, with 2 of those over 39°C and as such would be considered **hyperthermic** (see Figure 2). Of the 14 **hyperthermic** PICU arrivals, 1 died 2 weeks following surgery from heart failure. This preliminary data demonstrates a significant need for better post-operative temperature management as it is well established in the traumatic brain injury and stroke literature that **hyperthermia** is associated with worse outcomes. This preliminary data also suggests that by rewarming to 36-36.5°C according to the current institutional protocol on cardiopulmonary bypass, at least one third of infants then develop "overshoot" of their temperature beyond 37°C. This post-operative **hyperthermia** may also be corrected with use of the delayed rewarming strategy proposed in this project and as such is a potentially modifiable source of neurological injury.

MATERIALS AND METHODS

Subjects and study design: 30 infants under the age of 12 months with congenital heart disease requiring cardiopulmonary bypass surgery will be recruited for this study. The experimental treatment is “delayed rewarming” and will be defined as the cessation of rewarming on cardiopulmonary bypass at 35°C (see Figure 3). During both phases, there will be 12 hours of controlled rewarming to 36.5°C and the temperature will be maintained at 36.5 C for the 12 hours after rewarming . All types of congenital heart disease requiring cardiopulmonary bypass and intraoperative hypothermia will be considered for enrollment including (Tetralogy of Fallot (TOF), Arterioventricular canal (AV canal), Hypoplastic left or right heart (HLHS), Transposition of the Great Arteries (TGA), Truncus arteriosus (TA) and Total Anomalous Pulmonary Venous Return (TAPVR). Exclusion criteria include a pre-existing coagulopathy or cardiac lesions not requiring hypothermia and bypass and these include Atrial Septal defect (ASD), Ventricular Septal Defect (VSD), Patent Ductus Arteriosus (PDA) and Coarctation of the Aorta (Coarc). Exclusion criteria also includes the inability to wean from bypass following surgery. This is a randomized pilot study primarily assessing the safety of the delayed rewarming technique and secondarily assessing levels of serum biomarkers for neuronal injury at the 4 intervals shown below (see Figure 3).

Figure 3a: Research design for pilot

[figure not shown]
[figure not shown]

Figure 3b: Research design for KL2 project

Randomization: We will randomize in a one to one fashion. A random number generator will be used with those numbers being translated into a list of sequentially numbered opaque envelopes that will be opened by the principal investigator (PI) in order at the time of randomization following the informed consent process.

Recruitment: [name] and [name] are pediatric cardiologists and follow expectant mothers weekly or biweekly throughout a pregnancy known to be complicated by a diagnosis of congenital

heart disease. [name] and [name] will refer appropriate patients to [name] (PI) for consideration of enrollment. The PI will meet with the pregnant mother and father in the outpatient setting several weeks after the diagnosis has been made, giving the family time to come to terms with this new diagnosis. At the first meeting with the PI, the family will be informed about the research study and given informational handouts. Another meeting will occur prior to the admission during which the congenital heart surgery will be performed. At this second meeting, informed consent documentation will be reviewed and signatures obtained from parents willing to participate. For infants who need congenital heart surgery within the first few days of life or for those in whom a fetal diagnosis was not made, the PI will obtain informed consent from parents in the hospital prior to surgery. The envelopes for randomization will be opened at the time consent is obtained to insure that there is adequate time to arrange for the type of post-operative care the infant will receive (intervention versus standard of care).

Standard of care group: For infants assigned to the standard of care group, the congenital heart surgery will be performed according to usual practice with the degree of intra-operative hypothermia determined by the cardiothoracic surgeon and his team based on the anticipated complexity of the case. Following completion of the surgical procedure, the infant will be rapidly rewarmed on cardiopulmonary bypass at a rate of 1°C each 3-5 minutes. The infant will achieve normothermia of 36-37°C and be transported to the Pediatric Intensive Care Unit (PICU) for routine post-operative monitoring. Standard of care procedure in the post-operative setting is clearly defined below on Figure 4.

Figure 4: Standard of Care Temperature Management after Bypass

LOCATION	PERSON RESPONSIBLE	RECORDING SITE	GOAL TEMP	FACTORS
Operating Room	Anesthesiologist	Nasopharyngeal	36-37°C	
 1. Bair Hugger: consider 38°C setting rather than 43°C setting 2. Blood products do not necessarily have to be warmed prior to administration-titrate to infant temperature 3. iv Tylenol administered in the OR (10 mg/kg)
Transport to PICU	Anesthesiologist	Nasopharyngeal	36-37°C	
 1. Do NOT automatically place warm blankets on infant 2. OR room temperature should be >73°F (23°C) to reduce radiation and convection losses 3. Anesthesiologist to continue Nasopharyngeal temperature monitoring until the infant is departing for PICU
PICU	CT surgeon and/or PICU attending	Esophageal	36-37°C	
 1. Monitor temperature continuously-record hourly 2. Room temperature >73°F (23°C) 3. Tylenol orders placed for ongoing therapy (+6 hours from dose given in OR)
If infant develops HYPOthermia (CORE temp <36°C)				
 1. Apply Bair hugger and set to 38°C 2. Close doors to room 3. Increase ambient room temperature >75°F 4. Call CT surgeon/PICU Attending for temperature <35.5°C
If infant develops HYPERthermia (CORE temp >37.0°C)				
 1. Remove blankets on infant 2. Check room temperature-decrease if necessary 3. If temperature climbs to >37.0°C, apply ice packs to axilla and groin, recheck temp Q 15 min, remove ice when temperature <37°C again 4. Call CT surgeon/PICU attending for temperature > 37.5°C

Routine monitoring includes careful observations of the following parameters:

1. Hemodynamic status- The components of hemodynamic status that are continuously monitored in the postoperative setting include heart rate, rhythm and blood pressure. In the post-operative setting, telemetry (continuous heart rate monitoring) is standard on all congenital heart patients and all patients have arterial lines placed for continuous blood pressure monitoring. These are direct measures of hemodynamic status and are continuously uploaded to the electronic medical record on a minute to

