Experimental group: For infants assigned to the experimental group, the congenital heart surgery will be performed according to usual practice as detailed in the standard of care group section above, with depth of hypothermia dictated by the complexity of the congenital heart lesion to be repaired. Upon completion of the surgical procedure, partial rewarming will occur on cardiopulmonary bypass, but will stop when the infant reaches 35°C.

The infant will be transported from the operating room to the PICU at 35°C and placed on a servo-controlled blanket with an esophageal temperature probe placed. Through use of the servo-controlled blanket, the rate of rewarming will be carefully regulated with increases in temperature of 0.3°C every 2 hours for 6 and then of 0.2°C every 2 hours for 6 hours to the goal temperature of 36.5°C (see Appendix 1 for temperature management worksheet phase 1). The intensity and frequency of post-operative monitoring will be exactly the same in the experimental group as in standard of care group, including post-operative EEG, serum biomarker testing and neurodevelopmental follow up. The following parameters will be observed in the experimental group and compared with the standard of care group.

1. Hemodynamic status-Infants who are hypothermic typically have lower resting heart rates than those who are normothermic (80-100 beats per minute versus 120-140 beats per minute respectively). In the post-operative congenital heart infant, bradycardia (slow heart rate) could conceivably have an adverse impact on the hemodynamic status of the infant and if untreated this could also impact renal function. Hemodynamic status will be continuously monitored in the same manner as detailed in the standard of care section. Intravenous medications to support cardiac function and blood pressure (which these infants are typically already treated with) will be up-titrated if necessary. The need for permanent pacemaker implantation will be documented.

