In order to carefully define what is considered an adverse event, a retrospective chart review was performed for 15 infants in the past 12 months who survived congenital heart surgery with cardiopulmonary bypass at MMC. Of the 15 infants, the mean age at the time of surgery was 148 days with a range from 4 to 356. Of the 15 infants, 10 were male and 5 female. These infants had a mix of cardiac lesions similar to those who would be enrolled in this study. See Table 1 for a full outline of parameters that will be considered acceptable for infants enrolled in the study, which are based on the retrospective review of 15 survivors. Using these parameters to define what has been previously consistent with “safe”, any infant enrolled in the proposed study with results outside these parameters will then be considered as an adverse event and the data safety monitoring board will be informed. If a severe adverse event occurs in either Phase 1 or Phase 2 of the proposed research protocol, no additional infants will be enrolled and all experimental exposures will be suspended until a decision is made by the DSMB.

Table 1: Definitions of Serious, Moderate and Other Adverse Events

Serious Adverse Events	Reported to DSMB within 24 hours of occurrence
Mortality	Death within 48 hour period following surgery
Need for resuscitation	Need for cardiopulmonary resuscitation within 48 hours of surgery
ECMO after surgery	Persistent need for bypass (ECMO) following surgery; STUDY EXCLUSION CRITERIA
Return to OR on day of surgery	Unexplained hemorrhage prompting return to the OR for exploratory surgery
Stroke or seizures	Ischemic or hemorrhagic stroke OR status epilepticus OR clinical or electrographic seizures
Moderate Adverse Events	Reported to DSMB within 48 hours of occurrence
Bradycardia	Clinically significant heart rate <100 bpm for >30 minutes*
Tachycardia	Clinically significant heart rate > 160 bpm for 30 minutes*
Arrhythmia (JET)	Any occurrence of JET(Junctional ectopic tachycardia) OR other arrhythmia
Hypotension	Systolic BP< 70 mm Hg OR Diastolic BP< 30 mm Hg *
Coagulopathy	INR > 2.2 OR PTT > 74 seconds Thrombocytopenia with platelets < 50,000 Chest tube output more than 5 cc/kg/hr OR 40 cc/kg in an 8 hour shift
Leukopenia	White blood cell count < 4,000
Other adverse Events	Reported to DSMB within 7 days

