Data will be collected at the bedside and through chart review. A study ID number will be assigned to each infant and study documents will all use this ID number to combine data. Identifiable data will be stored separately. Preoperative (baseline) variables including gender, age in months and type of congenital heart lesion will be collected. A baseline s100b and NSE will also be considered pre-operative variables. Intraoperative variables including aortic cross clamp time, cardiopulmonary bypass time, lowest temperature during surgery, time for rewarming on bypass in all 3 groups and s100b and NSE at the completion of cardiopulmonary bypass will be collected. Postoperative variables include temperature, heart rate, blood

pressure, presence or absence of an arrhythmia such as JET, pressor use, frequency of transfusions, hours of intubation, coagulation dysfunction, frequency and type of infection and presence or absence of subcutaneous fat necrosis for 48 hours after surgery. S100b and NSE will be compared at the 4 post-operative time points as well.

Success of randomization will be assessed by comparing baseline characteristics in the two treatment groups; we acknowledge that randomization may not be entirely effective with such a small sample size and we will examine the data for biases to be considered in interpreting our findings. For this safety study, primary outcomes will be composite outcomes and will include the frequency of serious adverse events as well as the frequency of any adverse events (see Table 1) and will be compared among treatment groups using chi square tests or Fisher's exact tests, as appropriate. The frequency of individual adverse events such as hemodynamic compromise, arrhythmia, coagulopathy, infection, hyperthermia and subcutaneous fat necrosis will also be examined. Biomarkers (s100b and NSE) will be examined using a repeated measures analysis of variance, with the time * treatment interaction serving as the hypothesis test.

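### Failure to wean from bypass (ECMO) is both an exclusion criterion and a primary-outcome serious adverse event, and it is known only after randomisation

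*Combined protocol and SAP*

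**What the plan says.** Under Materials and Methods (Subjects and study design), the protocol states: "Exclusion criteria also includes the inability to wean from bypass following surgery". Table 1, printed under Anticipated outcomes and again in the Data Safety and Monitoring Plan, places ECMO after surgery among the serious adverse events and defines it as "Persistent need for bypass (ECMO) following surgery; STUDY EXCLUSION CRITERIA". The same row therefore carries both labels. The exclusion list under Recruitment plan and consent procedure does not mention failure to wean, so the two exclusion lists differ.

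The Analysis section says that "primary outcomes will be composite outcomes and will include the frequency of serious adverse events as well as the frequency of any adverse events", with reference to Table 1. It names chi-square or Fisher's exact tests. It defines no analysis population, and neither it nor any other section says whether an infant excluded after randomisation is counted or replaced.

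On timing, the Recruitment section says: "The envelopes for randomization will be opened at the time consent is obtained". Consent is obtained before surgery, including for urgent cases. The Randomization section has the principal investigator open the envelope, and no blinding is described.

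**The concern.** An exclusion criterion normally decides who enters a trial. This one can be assessed only after the infant has been randomised, operated on and treated according to arm, so in practice it is a rule for removing infants after randomisation. The event that triggers removal is one of the five serious event types in Table 1 and so part of the primary outcome.

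Specific Aim 1 asks whether the delayed group has no higher frequency or severity of adverse events. Under Human Subjects Involvement, the larger efficacy trial depends on safety being shown first. If infants who need ECMO are dropped, the serious-event frequency is understated in any arm where ECMO occurs. Any other adverse event in those infants also leaves the second composite.

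**Working it through.** **Sequence of events.**

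1. Consent is obtained and the envelope is opened, so the arm is known (Randomization; Recruitment).
2. Surgery takes place on bypass.
3. The arms diverge while the infant is still on bypass. In the standard arm "the infant will be rapidly rewarmed on cardiopulmonary bypass at a rate of" 1°C per 3-5 minutes, to 36-37°C. In the experimental arm "partial rewarming will occur on cardiopulmonary bypass, but will stop when the infant reaches" 35°C.
4. Only then is it known whether the infant can be weaned.
5. In the experimental arm, the infant goes to the PICU and is "placed on a servo-controlled blanket with an esophageal temperature probe placed".

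Any exclusion at step 4 therefore follows both randomisation and the start of the treatment difference.

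**Three ways to apply the text.**

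- The event is counted and the infant continues.
- The event is counted and the infant only leaves the remaining study procedures (step 5 onward).
- The infant is excluded, and the event leaves both numerator and denominator.

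The first two give the same primary-outcome table, provided data collection continues. The third is the ordinary meaning of an exclusion criterion, and the Analysis section does not rule it out.

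**Inputs.** Adequacy of sample gives 30 infants, 15 per arm (30/2 = 15). There is no power calculation to reproduce, because the plan states that it lacks the power for definitive analysis. No ECMO rate is given, so every rate and count below is assumed.

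**Chance that the problem arises.** P(at least one case in 30) = 1 − (1 − r)^30:

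- r = 1%: 1 − 0.99^30 = 0.260
- r = 2%: 1 − 0.98^30 = 0.455
- r = 5%: 1 − 0.95^30 = 0.785

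**Effect on the reported frequency.** ECMO occurs in the delayed arm only and there are no other serious events. Intervals are two-sided 95% Clopper-Pearson; for 0/n the upper limit is 1 − 0.025^(1/n), for example 1 − 0.025^(1/14) = 23.2%. Fisher p is two-sided, against 0/15 in the standard arm, with nobody removed.

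| ECMO cases | Counted | Fisher p | Excluded | Upper limit |
|---|---|---|---|---|
| 1 | 1/15 = 6.7% (0.2-31.9%) | 1.000 | 0/14 | 23.2% |
| 2 | 2/15 = 13.3% (1.7-40.5%) | 0.483 | 0/13 | 24.7% |
| 3 | 3/15 = 20.0% (4.3-48.1%) | 0.224 | 0/12 | 26.5% |

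With one case in each arm, 2/30 (6.7%, 0.8-22.1%) becomes 0/28 (upper limit 12.3%). The arms still look equal, but the trial reports no serious events.

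**Effect on the test.** Exclusion can move the p-value in either direction, though crossing 0.05 takes extreme counts:

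- 5/15 v 0/15 has p = 0.042. If two of the five are ECMO and are removed, 3/13 v 0/15 has p = 0.087.
- 5/15 v 1/15 has p = 0.169. If the single standard-arm event is ECMO and is removed, 5/15 v 0/14 has p = 0.042.

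After a severe adverse event the protocol says "no additional infants will be enrolled and all experimental exposures will be suspended until a decision is made by the DSMB". Every scenario with more than one serious event therefore assumes that enrolment was allowed to resume, repeatedly so for the five-event examples.

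**The case against.** The strongest reply is that the text, read as a whole, favours counting. The Analysis section points to Table 1, and Table 1 lists ECMO as a serious event; a row that could never be counted would be pointless. The omission of failure to wean from the recruitment-section exclusion list also fits the view that it only ends the remaining study procedures. Those are fair reasons to think counting may be intended. They do not settle the matter, because the same Table 1 row carries the exclusion label and the study-design section states the exclusion outright.

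A second reply is that each case goes to the DSMB within 24 hours and pauses enrolment, so it cannot disappear. That holds for protecting infants during the trial, but it does not decide who appears in the final between-arm table.

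Third, the pilot disclaims power and states no alpha, so a p-value crossing 0.05 decides nothing. This stands: the damage is to the count and the estimate, roughly 7 percentage points in one arm per case. With 15 infants per arm, however, those counts are the evidence on safety.

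Fourth, persistent need for bypass is a clinical event, and the documents do not say who would apply the exclusion or whether there is discretion. This also stands. Knowledge of the arm makes the rule harder to defend, but there is no evidence that it would be misused.

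**Conclusion.** The concern holds, and the text should be corrected before analysis. A stated rule, applied as written, removes a primary-outcome event and its infant from the safety comparison after randomisation and after treatment has diverged. One excluded case can turn 1/15 into 0/14, so that an arm with a serious event is reported as having none.

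Three limits apply. The consequence depends on ECMO occurring, at a rate the documents do not give, and on the exclusion being applied literally. Nothing in the documents links stopping at 35°C to failed weaning, so the direction of any bias is unknown. Statistical significance would usually be unaffected.

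**What to change.** Reconcile the exclusion criteria in Subjects and study design, both printings of Table 1, and the list in Recruitment plan and consent procedure, so that failure to wean or ECMO is not a reason for removal from the analysis. Add to the Analysis section:

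> Every randomised infant who goes on bypass is included in the safety analysis in the assigned arm and is not replaced. ECMO after surgery is counted as a serious adverse event in the primary outcome and reported by arm, even if the infant does not continue the remaining study procedures. Randomised infants who do not go on bypass are listed by arm with the reason.

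This population is fixed before rewarming differs between arms, and the final sentence keeps the remaining randomised infants visible. The wording leaves clinical management unchanged.

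The cost is wording only. It needs no new data, visits or infants, since Table 1 already requires ECMO to be reported to the DSMB within 24 hours.

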1. Electroencephalogram (EEG) will be performed in the immediate 48 hours following surgery to monitor for the occurrence of seizures. EEG leads are applied to the scalp of the infant and are non-invasive. The infant will have residual effects of anesthesia from surgery and is unlikely to experience any discomfort from the application of the electrodes on the scalp. The EEG will be remotely assessed by the PI at a minimum of 3 times per 24-hour period. Current American Clinical Neurophysiology Society guidelines recommend a minimum of 2 daily EEG assessments²⁶. If seizures occur, the EEG recording will be marked for seizure onset and seizure end so that the total duration of seizures in seconds may be calculated. If seizures are detected in either standard of care or delayed rewarming groups, they will be treated according to established guidelines which include administration of a standard loading dose of phenobarbital (20 mg/kg) followed by a second loading dose of phenobarbital in the event of persistent seizure activity. In the unlikely scenario that seizures are still present, Fosphenytoin would be administered in a 20 mg/kg loading dose. The type of medications administered including dose and timing of administration will be recorded in the electronic medical record and compared between groups.
2. Residual blood that would otherwise be wasted from a clinically obtained sample will be collected and used for testing for biomarkers of neuronal injury (s100b and NSE). These samples will be obtained at the following 5 intervals; the pre-operative setting for baseline, post-operatively after bypass, at post-op hour 24, at post-op hour 48 and at post-op hour 72. [name], Research Program Director of the BioBank and Research Laboratory Services (RLS) at Maine Medical Center Research Institute has kindly agreed to assist with technical support for the processing of the s100b and NSE testing. The s100b testing is a serum ELISA test run on a kit provided by Millipore™. This test requires 100µL of serum per sample to be tested. This ELISA may be run on a sample that has been previously frozen. The NSE test is also run on serum and is an ELISA test requiring 100µL of serum that may also be used on a frozen stored specimen. The company providing the NSE sample kit is R&D Systems. The stored samples will then be run in batches once the full collection period is complete. The collection of the samples and the handling of samples will be facilitated by the PI and [name], research

coordinator participating in the project (please see the attached letter of support from [name], VP Neuroscience Service Line who is funding the research coordinator position).

3. Bayley Infant Scales of Development (Bayley 3) will be performed between age 9 months and 2 years. The testing will be performed by a physical therapist who assesses fine and gross motor indices and by a Master's level psychologist who assess both the cognitive and language development components. Severe developmental disability will be defined as a Bayley Mental Development Index score that is 2 standard deviations below the mean score (eg. below 70)⁵. Moderate developmental disability will be defined as a Bayley Mental Development Index score that is 1 to 2 standard deviations below the mean score (eg. below 70-84)⁵. The parents of research subjects will have the opportunity to meet with a member of the developmental assessment team to review results of the testing.

Experimental group: For infants assigned to the experimental group, the congenital heart surgery will be performed according to usual practice as detailed in the standard of care group section above, with depth of hypothermia dictated by the complexity of the congenital heart lesion to be repaired. Upon completion of the surgical procedure, partial rewarming will occur on cardiopulmonary bypass, but will stop when the infant reaches 35°C.

The infant will be transported from the operating room to the PICU at 35°C and placed on a servo-controlled blanket with an esophageal temperature probe placed. Through use of the servo-controlled blanket, the rate of rewarming will be carefully regulated with increases in temperature of 0.3°C every 2 hours for 6 and then of 0.2°C every 2 hours for 6 hours to the goal temperature of 36.5°C (see Appendix 1 for temperature management worksheet phase 1). The intensity and frequency of post-operative monitoring will be exactly the same in the experimental group as in standard of care group, including post-operative EEG, serum biomarker testing and neurodevelopmental follow up. The following parameters will be observed in the experimental group and compared with the standard of care group.

1. Hemodynamic status-Infants who are hypothermic typically have lower resting heart rates than those who are normothermic (80-100 beats per minute versus 120-140 beats per minute respectively). In the post-operative congenital heart infant, bradycardia (slow heart rate) could conceivably have an adverse impact on the hemodynamic status of the infant and if untreated this could also impact renal function. Hemodynamic status will be continuously monitored in the same manner as detailed in the standard of care section. Intravenous medications to support cardiac function and blood pressure (which these infants are typically already treated with) will be up-titrated if necessary. The need for permanent pacemaker implantation will be documented.

Normothermic or hyperthermic post-operative congenital heart infants may experience a cardiac arrhythmia following surgery known as junctional ectopic tachycardia (JET). JET is a surgical complication that is concerning due to the fact that the newly repaired heart is beating significantly faster than it is intended to, adding significant strain to the heart muscle and potentially compromising hemodynamic stability. One of the treatments for JET is to reverse **hyperthermia** (this is only an option if the patient has a fever) or potentially even use **hypothermia** for refractory cases. We will monitor carefully to determine whether or not there is a decreased incidence of JET in the experimental group.

2. Coagulopathy- In adults who undergo therapeutic hypothermia following cardiac arrest, there is evidence of coagulation dysfunction and subsequent risk of bleeding. This tends to not be the case in infants who tolerate therapeutic hypothermia better than adults. Laboratory screening for coagulopathy will occur as described in the standard of care group and if coagulopathy develops, blood products (Platelets or Fresh Frozen Plasma or Cryoprecipitate) will be administered to reverse this. Chest tube output will also be carefully monitored in cc/kg/hour and the number of days a chest tube is in place will also be recorded .
3. Infection- In adults, there is evidence for increased rate of ventilator acquired pneumonia in patients undergoing therapeutic hypothermia after myocardial infarction. Again, this is unusual in infants who

tolerate hypothermia better. The infants in this study will receive daily chest x-rays in the post-operative setting and signs of infection will be carefully monitored for and antibiotics started if necessary.

4. **Hyperthermia**-The infant's temperature will be closely monitored during rewarming and for 48 hours afterward. An esophageal probe must be used during rewarming due to the fact that a skin or rectal recording is less accurate with hypothermic patients.
5. **Subcutaneous fat necrosis**-In infants who are exposed to a full 72 hours of therapeutic hypothermia, there is a rare complication of breakdown of the fat stores in the skin leading to the formation of fluid filled nodules in the skin that are unsightly but not life threatening. These nodules typically resolve without intervention over the weeks following the hypothermia exposure. Good hemodynamic status is protective against this complication. It is expected that the short duration of rewarming (only 12 hours) will not cause any incidents of subcutaneous fat necrosis.

Anticipated outcomes: The primary outcome variable is safety of the delayed rewarming technique which will be determined by the occurrence of adverse events in the standard of care versus delayed rewarming group. Specifically, clinically significant changes in the hemodynamic status of the infant, coagulopathy, infection or the presence of subcutaneous fat necrosis will be evaluated (see Table 1 for full definitions of all parameters). The secondary outcomes include the comparison of serum biomarkers (s100b and NSE), EEG findings including seizure frequency and developmental outcome assessments in the standard of care versus delayed rewarming group. It is anticipated that the delayed rewarming technique will be safe and that a trend will be seen toward lower level of s100b and NSE in the delayed rewarming groups, although this study is not powered to definitively assess this. Given that this project is considered more than “minimal risk”, a data safety monitoring plan has been developed (see attached DSMB plan). The DSMB will determine whether or not an adverse event is clinically significant and whether or not it is attributable to the delayed rewarming intervention. The PI will report any adverse event to the monitoring entity with 24 hours.

In order to carefully define what is considered an adverse event, a retrospective chart review was performed for 15 infants in the past 12 months who survived congenital heart surgery with cardiopulmonary bypass at MMC. Of the 15 infants, the mean age at the time of surgery was 148 days with a range from 4 to 356. Of the 15 infants, 10 were male and 5 female. These infants had a mix of cardiac lesions similar to those who would be enrolled in this study. See Table 1 for a full outline of parameters that will be considered acceptable for infants enrolled in the study, which are based on the retrospective review of 15 survivors. Using these parameters to define what has been previously consistent with “safe”, any infant enrolled in the proposed study with results outside these parameters will then be considered as an adverse event and the data safety monitoring board will be informed. If a severe adverse event occurs in either Phase 1 or Phase 2 of the proposed research protocol, no additional infants will be enrolled and all experimental exposures will be suspended until a decision is made by the DSMB.

Table 1: Definitions of Serious, Moderate and Other Adverse Events

Serious Adverse Events	Reported to DSMB within 24 hours of occurrence
Mortality	Death within 48 hour period following surgery
Need for resuscitation	Need for cardiopulmonary resuscitation within 48 hours of surgery
ECMO after surgery	Persistent need for bypass (ECMO) following surgery; STUDY EXCLUSION CRITERIA
Return to OR on day of surgery	Unexplained hemorrhage prompting return to the OR for exploratory surgery
Stroke or seizures	Ischemic or hemorrhagic stroke OR status epilepticus OR clinical or electrographic seizures
Moderate Adverse Events	Reported to DSMB within 48 hours of occurrence
Bradycardia	Clinically significant heart rate <100 bpm for >30 minutes*
Tachycardia	Clinically significant heart rate > 160 bpm for 30 minutes*
Arrhythmia (JET)	Any occurrence of JET(Junctional ectopic tachycardia) OR other arrhythmia
Hypotension	Systolic BP< 70 mm Hg OR Diastolic BP< 30 mm Hg *
Coagulopathy	INR > 2.2 OR PTT > 74 seconds Thrombocytopenia with platelets < 50,000 Chest tube output more than 5 cc/kg/hr OR 40 cc/kg in an 8 hour shift
Leukopenia	White blood cell count < 4,000
Other adverse Events	Reported to DSMB within 7 days
Hypertension Pressor Use Days of intubation Infection Subcutaneous fat necrosis	Systolic BP > 100 mmHg OR Diastolic BP > 80 mmHg* Treatment with more than 2 pressors for more than 7 days Intubated for longer than 5 days Occurrence of urinary tract infection, pneumonia OR other wound infection Any occurrence

*resulting in hemodynamic compromise and/or need to administer medications to support heart rate and/or blood pressure

Regarding management of patients with complications from the delayed rewarming intervention, the most likely complication from the delayed rewarming intervention is bradycardia during the 12 hour rewarming period. Given that the post-operative temperature starts at 35°C, the bradycardia is likely to be minor. If bradycardia develops, providers at the bedside will assess the hemodynamic status of the infant. A determination will be made regarding whether or not the bradycardia is resulting in any degree of hemodynamic compromise. Hemodynamic compromise will be defined by bradycardia plus hypotension, poor renal function or oliguria. If there is hemodynamic compromise, then pressors will be titrated to increase the heart rate and blood pressure. These infants are typically already treated with two pressors in the immediate post-operative setting. Rapid rewarming may be considered if increasing pressors does not resolve the issue. In other populations of infants, however, rapid rewarming has been found to increase the severity of adverse events. Specifically, in term newborns with peripheral pulmonary hypertension, rapid rewarming exacerbates their condition by further diverting blood away from the lungs (to the large vascular bed in the skin that was just rapidly rewarmed). For this reason, rapid rewarming would only be used as a second step if pressor titration was not successful.

ANALYSIS

Data will be collected at the bedside and through chart review. A study ID number will be assigned to each infant and study documents will all use this ID number to combine data. Identifiable data will be stored separately. Preoperative (baseline) variables including gender, age in months and type of congenital heart lesion will be collected. A baseline s100b and NSE will also be considered pre-operative variables. Intraoperative variables including aortic cross clamp time, cardiopulmonary bypass time, lowest temperature during surgery, time for rewarming on bypass in all 3 groups and s100b and NSE at the completion of cardiopulmonary bypass will be collected. Postoperative variables include temperature, heart rate, blood

pressure, presence or absence of an arrhythmia such as JET, pressor use, frequency of transfusions, hours of intubation, coagulation dysfunction, frequency and type of infection and presence or absence of subcutaneous fat necrosis for 48 hours after surgery. S100b and NSE will be compared at the 4 post-operative time points as well.

Success of randomization will be assessed by comparing baseline characteristics in the two treatment groups; we acknowledge that randomization may not be entirely effective with such a small sample size and we will examine the data for biases to be considered in interpreting our findings. For this safety study, primary outcomes will be composite outcomes and will include the frequency of serious adverse events as well as the frequency of any adverse events (see Table 1) and will be compared among treatment groups using chi square tests or Fisher's exact tests, as appropriate. The frequency of individual adverse events such as hemodynamic compromise, arrhythmia, coagulopathy, infection, hyperthermia and subcutaneous fat necrosis will also be examined. Biomarkers (s100b and NSE) will be examined using a repeated measures analysis of variance, with the time * treatment interaction serving as the hypothesis test.

Additional project support: This clinical project will take place at Maine Medical Center in the Pediatric Intensive Care Unit. I have the support of [name], pediatric cardiothoracic surgeon, [name], chief perfusionist, [name], pediatric anesthesiology, [name], pediatric cardiology, [name], pediatric intensive care physician and [name], MMCRI. Please see the attached documentations of departmental support. I also have the support of the Pediatric Intensive Care Unit nurses and respiratory therapists who provide post-operative care for these infants. The equipment needed for implementing the delayed rewarming technique was purchased by Maine Medical Center for this research project. The disposable cooling blankets that the infants will be placed upon as well as the disposable temperature probes were purchased from the KL2 grant.

PROTECTION OF HUMAN SUBJECTS

Maine Medical Center (MMC) is committed to protect the rights and welfare of all research subjects. We received accreditation for our human research protection program (AAHRPP) in 2011. All investigators who are engaged in research are required to submit their research to our Institutional Review Board for review prior to conducting their research. We also provide a program for continued oversight and monitoring of all projects. Human Subject Protection and Health Information Privacy and Security training through CITI is a mandatory component of training for all personnel involved in this study as part of the Human Research Protection Program (HRPP) policy at Maine Medical Center. This research proposal, including recruitment materials and the informed consent will be submitted to the IRB for review and approval. This study will be performed in accordance with 45 CFR 46 subpart D, which applies to all research involving human subjects and additional protections for children involved as subjects in research, conducted, supported or otherwise subject to regulation by a federal department or agency.

